Any adverse events, serious adverse events, unanticipated problems involving risks to subjects, or other participant safety or data concerns will be reported to the on-site study coordinator and the PI by study staff within 48 hours of becoming aware of the event. Serious adverse events that could be related to the study and any study deaths (extremely unlikely) will be reported by the PI to the NIMH Program Officer immediately. In addition to serious adverse events, the following will be reported by the PI to the NIMH Program Officer: unanticipated problems involving risks to subjects, protocol violations (significant divergences from the IRB-approved protocol), non-compliance, and suspensions or terminations by monitoring entities (IRBs and the Zambian National Health Research Authority). Non-serious adverse events and unrelated serious adverse events will be reported in the annual progress report to NIMH. The PI will oversee follow-up on any safety concerns that arise and work with the Study Coordinator to ensure that participants in need of medical, legal, or psychosocial services receive

appropriate, timely referrals. The PI will adhere to the NIMH Reporting Policy (<https://www.nimh.nih.gov/funding/clinical-research/nimh-reportable-events-policy.shtml>).

E. Potential Scientific Problems:

Prior work indicates that couples' counseling interventions do not result in increased social harms.⁶³ Nonetheless, careful effort has been made to minimize, monitor, and address potential social harms. The intervention has been designed to minimize conflict within couples and ensure privacy. Because we are including women who may have experienced IPV, all activities have been designed in accordance with the WHO recommendations for conducting research on violence against women.⁶⁴ All potential risks will be described in the informed consent process. Participants in need of medical, legal, or psychosocial services will be given referrals. If recruitment at Chipata Clinic is not meeting enrollment targets, we will expand to other clinics in a step-wise manner. To address the potential problem of low male participation, we will offer group sessions on the weekends and the couples counseling sessions at flexible times to accommodate men's schedules; frame the intervention as "family health promotion;" and offer incentives at all sessions. Loss-to-follow-up could impact study success; however, we have accounted for this in our power analysis and applied key findings from the K99 phase to ensure that the intervention is acceptable to maximize retention.

F. Data Analysis Plan:

1. Statistical analysis: In order to evaluate if the intervention has an effect on women's viral suppression (<1000 RNA copies/ml),⁶⁰ all female participants will have their research-only blood drawn at baseline (pregnancy), 6 weeks postpartum, and 24 weeks (6 months) postpartum. Blood will be collected at UTH, which has an existing infrastructure capable of testing women's viral loads in their laboratory. In addition, we will conduct behavioral surveys with female and male participants, separately, at baseline and at 6 weeks and 24 weeks postpartum. The survey draws upon existing validated measures, such as the ART visual analog scale⁶¹ and the Revised Conflict Tactics Scale⁶² and is informed by my extensive preliminary work during the K99 phase. All data will be entered into pre-programmed tablets by trained research assistants using REDCap. Data will be exported into STATA 14 and MPlus for analysis (see table below).

Data Analysis Plan

Aim	Indicators		Data source	Analytic method
Aim 1: Compare service utilization and PMTCT outcome indicators in two study conditions	Primary outcome: female viral suppression at 24 weeks postpartum (<1000 RNA copies/ml)	Intermediate outcomes: 
 ➤ female viral suppression at 6 weeks postpartum ➤ female self-reported ART adherence (visual analog scale using 3-day, one-week, and one-month recall periods) ➤ facility birth ➤ exclusive breastfeeding to six months ➤ uptake of pediatric HIV testing (and treatment if positive) ➤ postpartum family planning 	Research-only blood draws (female partner), + Behavioral surveys	Independent t-tests and Pearson's chi-square tests; logistic regression models with generalized estimating equation; survival analysis with cumulative incidence across time, Kaplan-Meier curves, mixed-effects Cox proportional hazards models
Aim 2: Establish the effect of the	Intrapersonal mechanisms: 
 ➤ mental health 	Interpersonal mechanisms: 
 ➤ IPV past month ➤ Intimacy and trust 	Behavioral surveys	Mediation analysis with structural equation modeling

intervention on intra- and inter-personal mechanisms influencing PMTCT outcomes	
 ➤ self-esteem ➤ perceived stigma ➤ perceived partner acceptance 	
 ➤ Communication skills ➤ problem-solving skills ➤ joint decision-making ➤ Conflict resolution skills ➤ Relationship satisfaction ➤ Perceived social support ➤ Communal coping 		(SEM)
--	---	---	--	-------

2. Sample size calculation: Based on the primary outcome (viral load) and a projected 25% loss to follow-up (10% due to break-ups and 15% due to other causes), we require 238 total couples (119 couples per arm) to achieve the sample size target of 178. This target is based on a Pearson's chi-squared two-sample proportions test with a power of 0.80 and alpha of 0.05, assuming a delta of 0.20 at the 6-month follow-up between the intervention and control arms. Based on recent studies from the region,⁵⁸⁻⁶⁰ we estimate viral suppression at 6-months to be 55% in the control arm and 75% in the intervention arm. For the intermediate and mediating variables on the behavioral survey, the proposed sample size will enable us to detect a hazard ratio of 0.75, power of 0.80, and alpha of 0.05, using a two-sample comparison of survivor functions exponential test.

G. Summarize Knowledge to be Gained:

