Aim 2: Establish the effect of the intervention on intra- and inter-personal mechanisms influencing PMTCT outcomes. *Approach:* I will measure critical intrapersonal factors among female participants (mental health, self-esteem, perceived stigma) and relationship dynamics (IPV, conflict resolution, communication, coping) that are hypothesized to be on the causal pathway between the intervention, PMTCT-related behaviors, and viral suppression. Data will be collected through behavioral surveys at baseline and at 6 weeks and 24 weeks postpartum. I will compare these dynamics between the intervention and control groups and will use mediation analysis and structural equation modeling to test whether these relationship dynamics are affected by the intervention and if they are underlying mechanisms linked to the study outcomes.

II. Background and Significance:

Prevention of mother-to-child transmission (PMTCT) programs have the potential to make substantial gains towards the UNAIDS 90-90-90 goals among pregnant and postpartum women living with HIV (WLWH).¹ However, progress in PMTCT has recently stagnated.⁸ Retention on lifelong antiretroviral therapy (ART), for instance, among pregnant and breastfeeding WLWH in sub-Saharan Africa is far too low; 20% of pregnant women who start ART drop out of care before delivery.⁸ In 2018, it was estimated that 16,000 pediatric HIV infections could have been averted if mothers in Southern Africa were retained on ART (out of 130,000 new pediatric HIV infections that year).⁸ Zambia is one of the countries in Southern Africa with the greatest burden of HIV among women of reproductive age³⁵ and accounts for 3% of the total new global pediatric HIV infections.⁸ In the country, more than 90% of pregnant women attend at least one antenatal care (ANC) visit and receive HIV testing (16% test positive).^{35, 36} Across the additional steps in the PMTCT continuum of care, however, women drop-off at alarming rates (Figure 1).^{3, 20, 21} Even among those who remain engaged in care, optimal viral suppression – a key predictor of mother-to-child transmission (MTCT) and HIV treatment success²²⁻²⁵ – is challenging, especially during the postpartum period.⁷ **Accelerated progress in keeping mothers alive and reducing the incidence of pediatric HIV is dependent on overcoming the critical challenges of ART adherence and sustained retention in care among pregnant and postpartum WLWH.**^{4, 20, 26, 27}

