IPV as a barrier to PMTCT adherence and retention: For my PhD dissertation and NIMH-funded F31 award, I led a mixed methods study in Zambia examining the relationship between gender power dynamics and HIV-positive women’s PMTCT adherence and retention. The results of this study indicate that HIV-positive pregnant and postpartum women in Zambia experience disproportionately high rates of IPV (>60%) compared to the general population of women.⁸ Moreover, women who experienced IPV, particularly emotional IPV, have reduced odds of adherence to ART during and after pregnancy,⁸ safe infant feeding,²⁷ and early infant HIV testing.¹⁸

Engaging men in PMTCT interventions: For my postdoctoral fellowship, I am leading a mixed methods study in western Kenya within the framework of my mentors' community randomized trial (R01HD0808477; PIs: [name], [name].). My sub-study examines the importance of specific male behaviors and relationship dynamics for PMTCT and ways to engage male partners in HIV care. The results from this research will help inform the specific content of the proposed K99/R00 couples counseling intervention.

IV. Research Methods

A. Outcome Measure(s):

The Primary outcome is the percent of female participants with HIV viral suppression (viral load <1,000 copies/mL) at 24 weeks postpartum between the intervention and control groups. The **Secondary outcomes** are the percent of female participants with HIV viral suppression (viral load <1,000 copies/mL) at 6 weeks postpartum; the percent of female participants reporting ART adherence (using validated instruments); facility birth; exclusive breastfeeding; pediatric HIV testing, diagnosis, and treatment uptake; and postpartum family planning between the intervention and control groups.

B. Description of Population to be Enrolled:

Couples are eligible if: female is <36 weeks pregnant (to have time to deliver at least one counseling visit during pregnancy); female is diagnosed as HIV-positive; both partners are >18 years of age and willing to participate; both partners live in the clinic catchment area and plan to reside there for at least six months; a long-term stable relationship (sleep under the same roof at least once a week) that has existed for ≥ 6 months; and no severe IPV in the past 6 months.⁶³

C. Study Design and Research Methods

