Couples counseling visit 3	Intervention couples	Love and support	
 ➤ Couple meets with a male-female pair of counselors ➤ 90-minute session focused on how couples can show love and support for one another

Data Collection: The following service utilization and PMTCT outcome data will be collected at baseline (pregnancy), 6 weeks postpartum, and 24 weeks postpartum: (1) women’s viral load testing (i.e., research-only blood draws at the University Teaching Hospital (UTH) laboratory); and (2) behavioral surveys.

Viral load testing (female participants only): we will collect research-only blood draws at baseline, 6 weeks postpartum (mid-line), and 24 weeks postpartum (end-line) to determine HIV treatment success via viral suppression (<1000 RNA copies/ml). Blood will be collected by health care workers at the UTH laboratory, which has an existing infrastructure capable of drawing blood and testing viral loads.

Behavioral questionnaires (all participants): We will administer face-to-face behavioral surveys to both female and male participants at baseline, 6 weeks postpartum (mid-line), and 24 weeks postpartum (end-line) to capture self-reported service utilization and PMTCT outcomes, hypothesized mediating variables (intrapersonal and interpersonal factors, including relationship dynamics), sociodemographic characteristics, and intervention experiences (if applicable). The surveys will be verbally administered to all enrolled WLWH (both control and intervention arms) and their male partners by trained Zambian research assistants in the local languages. Survey data will be entered on pre-programmed tablets using the REDCap (Research Electronic Data Capture) mobile application and sent to the secure host server at the University of Colorado Denver. REDCap is a secure, web-based application designed to support data capture for research studies, providing: 1) an intuitive interface for validated data entry; 2) audit trails for tracking data manipulation and export procedures; 3) automated export procedures for seamless data downloads to common statistical packages; and 4) procedures for importing data from external sources. Data can be entered and securely stored on the tablet and subsequently sent to the server upon internet connectivity, which makes its use ideal for low-resource settings.

D. Description, Risks and Justification of Procedures and Data Collection Tools:

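### The Aim 2 arm comparison and mediation model do not specify adjustment for baseline mediator values, although these are collected before randomisation

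*Combined protocol and SAP*

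**What the plan says.** Section I (Aim 2) lists surveys at baseline, 6 weeks and 24 weeks postpartum and then states the analysis: "I will compare these dynamics between the intervention and control groups and will use mediation analysis and structural equation modeling to test whether" the dynamics are affected by the intervention and underlie the outcomes. The Aim 2 row of the Data Analysis Plan table (IV.F.1) gives the method as "Mediation analysis with structural equation modeling" and nothing more. No equation, covariate, change score, or time point for mediator or outcome is named.

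The Data Collection text in IV.C includes "hypothesized mediating variables (intrapersonal and interpersonal factors, including relationship dynamics" in the questionnaire given at all three times. Under Procedures (IV.C), the baseline questionnaire is administered at the first group session. The opening of IV.C places randomisation after that session, so the baseline mediators are pre-randomisation values and valid covariates. The only stated use of baseline relationship values is to tailor counselling content (IV.C, The intervention).

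**The concern.** Randomisation makes the arms comparable for the effect of arm on the mediator and of arm on suppression. It does not make women with good and poor follow-up relationships comparable with each other. A couple who communicated well before enrolment will tend to do so at 6 or 24 weeks. If that same pre-existing quality also predicts suppression, an unadjusted model credits the follow-up mediator with an effect it may not have.

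The plan makes such a link plausible. Its central hypothesis ties better-functioning relationships to suppression, and Section III reports that "women who experienced IPV, particularly emotional IPV, have reduced odds of adherence to ART during and after pregnancy". If good relationships favour suppression, the bias runs towards declaring mediation.

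Mechanism is one of the trial's two aims, and Section G says the study will supply data for a larger trial, so a false mechanism could be carried into its design. The arm-to-mediator comparison would also be less precise than the collected data allow.

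**Working it through.** **1. The plan's own sample size.** IV.F.2 uses a "Pearson's chi-squared two-sample proportions test with a power of 0.80 and alpha of 0.05, assuming a delta of 0.20", and says "we estimate viral suppression at 6-months to be 55% in the control arm and 75% in the intervention arm". With a pooled rate of 0.65 and a two-sided test:

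n per arm = [1.96·√(2·0.65·0.35) + 0.8416·√(0.55·0.45 + 0.75·0.25)]² / 0.20² = (1.322 + 0.555)² / 0.04 = 88.1, so 89 per arm and 178 in total.

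With 25% loss, 178/0.75 = 237.3, so 238. This matches "we require 238 total couples (119 couples per arm) to achieve the sample size target of 178". The checks below use 89 per arm.

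**2. Inputs the documents do not give (assumptions).**
- Baseline-to-follow-up correlation r of the mediator: 0.3, 0.5, 0.7.
- Log-odds g of suppression per SD of the baseline mediator: 0.2 (weak), 0.4 to 0.7 (moderate to strong).
- Arm effect on the mediator: 0.42 SD, the difference with 80% unadjusted power, since (1.96 + 0.8416)·√(2/89) = 0.42.

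**3. Arm-to-mediator comparison.** Adjusting for baseline multiplies the residual SD by √(1 − r²), so power = Φ(0.42·√(89/2)/√(1 − r²) − 1.96), where 0.42·√44.5 = 2.80.
- Unadjusted: Φ(0.84) = 80%.
- r = 0.3: Φ(2.80/0.954 − 1.96) = Φ(0.98) = 84%.
- r = 0.5: Φ(2.80/0.866 − 1.96) = Φ(1.27) = 90%.
- r = 0.7: Φ(2.80/0.714 − 1.96) = Φ(1.96) = 98%.

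**4. Size of the confounding.** Within an arm, the expected baseline mediator given the follow-up mediator has slope r. A follow-up mediator with no effect therefore picks up a log-odds of roughly g·r. At r = 0.5 this is 0.4 × 0.5 = 0.20 (odds ratio 1.22) to 0.7 × 0.5 = 0.35 (odds ratio 1.42). Simulation gives 1.23 to 1.40, where the truth is 1.0.

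**5. False mediation, simulated.** n = 178; M0 ~ N(0,1); M1 = r·M0 + 0.42·arm + √(1 − r²)·e; logit P(suppressed) = 0.2 + 0.9·arm + g·M0, with no M1 effect. The intercept and arm term correspond to 55% and 75%: logit 0.55 = 0.20 and logit 0.75 = 1.10. Mediation is declared when both paths are significant at two-sided 0.05.

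| r | g = 0.2, no baseline term | g = 0.4 to 0.7, no baseline term | with baseline term |
|---|---|---|---|
| 0.3 | 5% | 8-16% | about 4-5% |
| 0.5 | 8% | 19-40% | about 4-5% |
| 0.7 | 12% | 32-62% | about 4-5% |

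Repeat runs differ from these by a few percentage points.

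**6. When the inflation disappears.** With no arm effect on the mediator, the unadjusted rate was 3.5% (r = 0.6, g = 0.8). With an arm effect of 0.2 SD and g = 0.4 it was 3-5% at r = 0.3 to 0.5.

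**7. Cost of adjusting when mediation is real.** Take an arm effect of 0.42 SD, a true mediator log-odds of 0.4, and a baseline value that acts only through the follow-up mediator. Power for the indirect effect, unadjusted then adjusted, is 54% and 54% at r = 0.3, 54% and 47% at r = 0.5, and about 52% and 38% at r = 0.7. It can also go the other way: with a 0.30 SD arm effect, log-odds 0.6 and r = 0.6 it rose from 49% to 57%.

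**The case against.** The plan is silent on baseline terms and does not exclude them. A reader might infer that the sponsor has decided to ignore the baseline mediators. The documents do not support that: baseline surveys are listed among the Aim 2 data, and a three-wave SEM could include them. What stands is that adjustment is not specified in the document that serves as both protocol and SAP, so the choice could be made after results are seen.

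A reader might also infer that chance imbalance between arms would be reported as mediation. It would not, beyond the nominal rate (step 6). The problem lies in differences between couples, on the mediator-to-outcome path, when the intervention does move the mediator.

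Nor is the confounder documented at any given size. Section III reports an association of IPV with adherence, without an effect size, without separating baseline from concurrent IPV, and without a suppression result. Eligibility requires a stable relationship and excludes recent severe IPV, which may narrow baseline variation. The value of g is therefore as much an assumption as r, and at g = 0.2 the harm is small.

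Finally, adjustment is not free and not complete. It can lower power for a true indirect effect (step 7). The 4-5% holds because the simulation makes the baseline mediator the only confounder and measures it without error. With an assumed baseline reliability of 0.7 and g = 0.7, adjusted false mediation is 10% at r = 0.5 and 17% at r = 0.7. All of these limits stand. They bound the size of the point but do not remove it.

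**Conclusion.** The concern holds as an unspecified adjustment with a known better choice, not as a decision to discard baseline data. The precision gain for the arm comparison depends only on r. The bias in the mediation claim needs three conditions together: the intervention moves the mediator, relationship quality persists, and baseline quality predicts suppression. Aim 2 hypothesises the first and the plan's rationale makes the third plausible, but the documents quantify none of them. The result should therefore be read as a range, from negligible to severe, and the upper figures need both a high correlation and a strong baseline effect. It would be too strong to say that omitting the baseline terms loses power for mediation in general, since the effect on that power can go either way. The primary viral suppression comparison and its sample size are unaffected.

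**What to change.** In the Aim 2 row of the Data Analysis Plan table, state that:
- each mediator at 6 and 24 weeks is compared between arms by regression on arm and the baseline value of that mediator;
- both SEM equations, for the mediator and for viral suppression, include the baseline value of that mediator, with baseline viral suppression as a further covariate.

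The cost is SAP wording and a few more model terms. All the values are already planned for collection at baseline, so no visit, sample or participant is added. The real downside is the possible loss of power for the indirect effect shown in step 7, which should be acknowledged when the choice is made. The text should also say that adjustment leaves other mediator-outcome confounders, and measurement error in the baseline mediator, unaddressed, so that a significant indirect effect is reported with that caution.

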This is a minimal risk study using a behavioral intervention to enhance HIV-related health behaviors and biomedical outcomes. The PI will be working with engaged staff at the University of North Carolina Global Projects Zambia (UNC GPZ) to implement the study. The proposed study uses a randomized controlled trial design (Phase II clinical trial) to test the efficacy of a couples counseling and health education intervention to change HIV-related health behaviors and biomedical outcomes (viral suppression) among pregnant and postpartum women living with HIV in Lusaka, Zambia. Our sample includes 238 heterosexual couples (n=476 individuals) recruited from the population of pregnant women living with HIV attending antenatal care at Chipata Clinic in Lusaka, Zambia. All enrolled couples (intervention and control groups) will be exposed to two group health education events. Couples in the intervention (n=119 couples) will additionally be exposed to three couples counseling visits. Biospecimen collection will take place in the form of three research-only blood draws to test viral loads among the female participants (n=238). We will also conduct face-to-face behavioral interviews using a standardized questionnaire. Recruitment and initial screening will take place during routine antenatal care (see Figure below). Local Zambian research assistants will work with nurses (relationship already established during the K99 phase) to conduct the initial screenings and recruit participants. Research assistants will arrange with interested, eligible women a convenient time and place to meet with them and their male partners (either the clinic or a private community venue) to complete the informed consent process, full screening, and enrollment. A letter will be offered to take home to the male partner explaining the study (women's HIV status will not be conveyed). Screening and informed consent will be done in separate locations for WLWH and their male partners (preferably at the same time) with gender-matched research assistants. Women with severe IPV will be offered support and referrals but will not be enrolled. Enrolled couples

will attend the first group education session (“baby shower” event) together during an upcoming weekend. Randomization into the intervention or control (n=119 couples per arm) will take place following the first group session using labeled envelopes.

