Procedures: We will schedule a series of 24 group education sessions across three months to take place on the weekends at community venues with an expected 10 couples in each group. The first baseline behavioral questionnaire will be administered during the group education session. All research assistants will be present at the scheduled group sessions to assist with the educational activities and administer the behavioral questionnaires. At this same time, we will collect baseline viral loads of pregnant WLWH. Couples in the intervention arm will subsequently receive three additional couples counseling sessions at a private community venue or the clinic (depending on participant preference): one during pregnancy (3rd trimester) and two postpartum (12 weeks and 18 weeks). Lay health workers will deliver the intervention and be supervised by a local study coordinator and the PI throughout the entirety of the project. The paired male-female counselors will work with each couple in the intervention. At 6 weeks postpartum, there will be a series of second group education sessions for all couples (intervention and control arms) and the mid-line behavioral questionnaire. The mid-line viral load will also take place at 6 weeks postpartum. At 24 weeks postpartum, we will collect the end-line behavioral questionnaires and viral load. Once data collection is complete, we will offer couples in the control arm the option to participate in a condensed (one-session) counseling intervention. We will not be assessing outcomes in the condensed intervention but thought it ethical to provide.

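### The six-month residence criterion has no stated starting point and, counted from enrolment in pregnancy, generally ends before the primary viral load at 24 weeks postpartum

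*Combined protocol and SAP*

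**What the plan says.** Section IV.B (Description of Population to be Enrolled) sets the residence rule: "both partners live in the clinic catchment area and plan to reside there for at least six months". It gives no anchor such as enrolment, birth or end of follow-up. The same section limits gestation only from above: "female is <36 weeks pregnant (to have time to deliver at least one counseling visit during pregnancy". No other criterion concerns staying until the end of follow-up.

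Enrolment and allocation both happen in pregnancy. Section IV.C states "Recruitment and initial screening will take place during routine antenatal care", and then "Randomization into the intervention or control (n=119 couples per arm) will take place following the first group session", which is the antenatal session.

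The endpoint is counted from birth. Section IV.A defines the primary outcome as the percentage of women with "viral suppression (viral load <1,000 copies/mL) at 24 weeks postpartum between the intervention and control groups", and the Procedures in IV.C say "At 24 weeks postpartum, we will collect the end-line behavioral questionnaires and viral load". Section IV.F.1 gives the postpartum draws as "6 weeks postpartum, and 24 weeks (6 months) postpartum", so there six months is measured from delivery.

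On attrition, Section IV.F.2 allows for a "projected 25% loss to follow-up (10% due to break-ups and 15% due to other causes"). Relocation is not named as a cause.

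**The concern.** A residence criterion in a longitudinal trial is there to select participants who expect to be present when the outcome is measured. This one is applied at screening in pregnancy, but its length matches the postpartum part of follow-up alone. The remaining weeks of pregnancy appear to have been left out. A couple who say at screening that they will leave in seven months meet the rule, yet at most eligible gestations they would be gone before the primary viral load.

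What is at stake is loss of the primary outcome that could be foreseen at screening and, for women enrolled earlier in pregnancy, loss of the later counselling visits at 12 and 18 weeks postpartum. The 25% allowance protects the number of evaluable women. It does not protect against bias if those lost differ in viral suppression, and Section IV.F names no method for a missing primary viral load.

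**Working it through.** **The plan's own figure.** Inputs from IV.F.2: suppression 55% against 75%, alpha 0.05 (taken as two-sided), power 0.80, equal arms, 25% loss. The Pearson chi-squared formula without continuity correction gives, per arm,

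[1.960 × √(2 × 0.65 × 0.35) + 0.842 × √(0.55 × 0.45 + 0.75 × 0.25)]² / 0.20² = 88.1, rounded up to 89.

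That is 178 evaluable, and 178 / 0.75 = 237.3, rounded up to 238. Both stated figures reproduce. Power at 89 per arm is 0.804.

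**Inputs for the time check.**
- Required residence: six months = 365.25 / 2 / 7 = 26.1 weeks, counted from enrolment (IV.B; this anchor is my reading).
- Gestation at enrolment: any value below 36 weeks (IV.B).
- Endpoint: 24 weeks after birth (IV.A, IV.C).
- Gestation at birth: not in the documents. I assume 40 weeks and show 37 to 41.

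**Formulas.** Weeks from enrolment to endpoint = (gestation at birth − gestation at enrolment) + 24. Postpartum week at which six months runs out = 26.1 − (gestation at birth − gestation at enrolment).

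**Results for birth at 40 weeks.**

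| Gestation at enrolment | Weeks to endpoint | Shortfall against 26.1 weeks | Six months runs out at postpartum week |
|---|---|---|---|
| 35 weeks 6 days | 28.1 | 2.1 | about 22 |
| 32 weeks | 32 | 5.9 | about 18 |
| 28 weeks | 36 | 9.9 | about 14 |
| 20 weeks | 44 | 17.9 | about 6 |

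**Sensitivity to the date of birth.** For the latest possible enrolment (35 weeks 6 days), the time to endpoint is 25.1, 26.1, 27.1, 28.1 and 29.1 weeks with birth at 37, 38, 39, 40 and 41 weeks. In general the endpoint falls within six months only if birth comes within 26.1 − 24 = 2.1 weeks of enrolment. In practice that means enrolment close to 36 weeks with birth at about 38 weeks or earlier, or a preterm birth soon after enrolment.

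**Counselling visits (birth at 40 weeks).** Six months ends before the 18-week visit if gestation at enrolment is below 40 − (26.1 − 18) = 31.9 weeks. It ends before the 12-week visit if gestation is below 40 − (26.1 − 12) = 25.9 weeks.

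**Illustration of what extra loss would cost.** These loss rates are hypothetical; the documents do not tie any of them to this criterion. With 238 couples, 30% loss leaves 167 evaluable and power 0.777; 35% leaves 155 and 0.746; 40% leaves 143 and 0.712. Each 5 points of loss is 0.05 × 238 = 11.9, or about 12 women.

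**The case against.** A reader might infer that the criterion builds missing primary outcomes into the trial, or leaves it underpowered. The documents do not support either reading, for these reasons.

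- The rule sets a minimum stay, not a departure date. Nothing says how many couples plan to leave between month six and the endpoint; it could be nearly none. No distribution of gestation at enrolment is given, so the 20-week case is illustrative.
- Leaving the catchment area is not the same as missing the blood draw. Outcome blood is taken at the University Teaching Hospital laboratory, not at the recruiting clinic, and no text withdraws couples who move. Someone who relocates within Lusaka could still attend.
- Loss is already budgeted at 25%, including 15% from causes other than break-ups, which is broad enough to include relocation. Section IV.E says loss was accounted for in the power analysis, and Section IV.D provides for regular monitoring of missing data, with action if follow-up rates threaten the research questions.
- A move already planned at screening precedes randomization, so it should balance between arms on average.
- The plan uses six months as shorthand for the postpartum endpoint. If the criterion was meant to run from birth, 26.1 weeks would cover week 24.

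The first three points stand, and they limit the consequence. The fourth holds for the intention to move. It does not settle whether movers still attend equally in both arms, since intervention couples have three extra contacts; the documents do not show a difference either way. The fifth shows that the anchor is ambiguous, but the criterion is applied in pregnancy and says nothing about birth, so the same edit is needed. None of these points explains why a rule meant to secure follow-up should stop short of the endpoint.

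**Conclusion.** The point holds as a mismatch in eligibility wording, of minor to moderate severity. Counted from enrolment, the most natural reading, the six months ends before the primary viral load for every eligible woman who gives birth at 40 weeks, by about 2 weeks at the latest enrolment and about 18 weeks for enrolment at 20 weeks' gestation. The exception is birth within about two weeks of enrolment. Couples who already plan to move before the endpoint are eligible, as are couples planning to move before the 18- or 12-week counselling visit if enrolled before about 32 or 26 weeks.

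This rests on two assumptions: that the clock starts at enrolment, and that pregnancy lasts about 40 weeks (37 to 41 shown). The resulting loss of primary outcomes cannot be sized from the documents. The sample size calculation is not in error.

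**What to change.** Reword the residence criterion in Section IV.B so that both partners plan to live in the catchment area until the 24-week postpartum visit. Calculate that date at screening as expected delivery date plus 24 weeks, and record it on the screening form. The documents define no visit window; if one is set, add it to the date.

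The cost is one eligibility line and one form field. The sample size stays at 178 evaluable and 238 enrolled. A few more couples would be screened out; the documents do not allow that number to be estimated, and Section IV.E already plans for possible recruitment shortfall. The criterion still rests on a stated intention, so it reduces foreseeable loss but does not guarantee retention. The change is most useful before enrolment begins.
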